STATISTICAL ANALYSIS PLAN

Evaluation of cigarette package inserts for enhanced communication with smokers

Principal Investigator [name], MA, MS, PhD

Professor, Department of Health Promotion Education & Behavior

Arnold School of Public Health University of South Carolina

Columbia, SC, USA

Clinicaltrials.gov identifier NCT04075682

Funding: National Cancer Institute/NIH (R01 CA215466)

Author [name]

Professor, Department of Epidemiology & Biostatistics

Arnold School of Public Health University of South Carolina

Columbia, SC, USA

Version December 13, 2022

SIGNATURE PAGE

Principle Investigator	[name] (12/13/2022)				
Author	[name]				
	[name] (12/13/2022)				

Table of Contents

1.	Study design overview	4
	Study hypotheses and outcomes	
	Assumptions for calculating power	
	Statistical design	
	Missing data	
	Sensitivity analyses	

This document is updated from the originally submitted version. Edits have been made to clarify which outcomes are associated with each hypothesis (Table 3), as this was not clearly indicated in the original submission. Also, we have revised the description of models for testing Hypotheses 5 and 6, whose original specification did not capture the contrasts intended in the original hypothesis wording (e.g., they evaluated differences in outcomes by participant characteristics but not moderation of treatment effects by participant characteristics). Why sensitivity analyses were limited to only one data type is also described.

Study design overview:

Experimental protocol: The basic design of the randomized controlled trial described as Study 1 follows a 2x2 between-subject treatment randomized assignment across whether there is an insert in the cigarette pack, and whether the health warning label includes pictures. We aimed to enroll a total of 380 persons to be randomly

assigned to the four treatment conditions. Given the expectation that 85% would complete the trial and provide adequate data for inclusion in the analyses, we expected to analyze data from 80 participants in each of the 2x2 treatment combinations (See Table 1).

 Table 1. Study 1 RCT design & sample allocation

 Randomized Participants
 Health warning label (HWL)

 Text only
 Text and Picture

 Yes
 80

 No
 80

 80
 80

Data types: Two types of data were collected, with different implications for power calculations due to the number of observations associated with each one:

- Type 1 data (daily log data) were collected from each person across a 2-week period yielding up to 14 repeated measures per person. Daily log data include a range of primary outcomes (e.g., foregoing cigarettes, talk about cessation) and secondary outcomes (e.g., cognitive elaboration of cessation benefits, perceived susceptibility) that encompass binary, ordinal and continuous variables.
- Type 2 data (event-based EMA) were collected approximately 4 additional occasions per day per person, yielding an average of 56 repeated measures of event-related data per person. Event-related data include both primary outcomes (e.g., feeling about smoking, self-efficacy to quit smoking, motivation to quit smoking) and secondary outcomes (e.g., hopefulness about quitting, satisfaction from smoking) measured as ordinal and continuous variables.

Study hypotheses and outcomes of interest:

Table 2 shows the study hypotheses. The outcomes evaluated depended on the specific hypothesis. Behavioral and psychosocial outcomes that are more proximal to cessation behaviors (e.g., foregoing/stubbing out cigarettes;

Table 2. Study 1 Hypotheses: EMA Randomized Controlled Trial

Main effects of condition on cessation-related outcomes & primary mediators

- **H1:** Exposure to packs with inserts will result in stronger efficacy beliefs (e.g., self-efficacy, response efficacy) than packs without inserts, which, in turn, will lead to stronger cessation-related outcomes (e.g., interpersonal discussions about quitting, foregoing cigarettes, reduced consumption, intention to quit).
- **H2:** Exposure to packs with large pictorial HWLs will produce stronger negative affective responses toward smoking than text-only HWLs, which, in turn, will lead to stronger cessation-related outcomes (see H1).

Interactions between inserts and HWLs & explanatory mechanisms

- H3: Insert effects on cessation-related outcomes (see H1) will be stronger when accompanied by pictorial HWLs than by text-only HWLs, because pictorial HWLs will promote greater attention to inserts ("spotlight" effect of negative affect).
- H4: Pictorial HWL effects (relative to text-only HWLs) on cessation-related outcomes (see H1) will be stronger when accompanied by inserts, because inserts will promote efficacy beliefs and thereby reduce defensive responding.

Interactions between condition & smoker characteristics

- H5: Pictorial HWL effects (relative to text-only HWLs) on key outcomes (see H1) will be moderated by baseline self-efficacy to quit, such that the association will be stronger amongst smokers whose baseline self-efficacy is higher than lower (H5a). Moderation effects will be weaker when packs include inserts (H5b).
- H6: Insert effects will be moderated by education, literacy, and delay discounting, such that the association with key outcomes (see H1) will be stronger for smokers with higher education, higher literacy, and lower delay discounting than for their counterparts (H6a). Moderation effects will be weaker when inserts are accompanied by pictorial HWLs due to because pictorial HWLs will have stronger effects among smokers with lower education and lower literacy (H6b).

motivation to quit) were assessed for all hypotheses. Other outcomes are specific to pathways of influence for insert effects or, separately, for pictorial HWL effects; hence, some outcomes were assessed only when they were relevant to the labeling effect (insert vs. pictorial HWL) evaluated in the hypothesis. Similarly, the proxy measure of "reactance" (i.e., expressed reactance) was only assessed for hypotheses assessing whether insert effects reduce defensive responding (i.e., H1, H4). Finally, the two outcomes involving positive smoking experiences (i.e., satisfaction, cognitive elaboration of smoking benefits) were only relevant to the main effects of pictorial HWLs (H2). Table 3 lists all primary and secondary outcomes, showing which were assessed for each hypothesis. Appendix 1 includes results for outcomes that are not specific to hypotheses (i.e., do not have an X in the table below). Details on the specific measures used and frequency of assessment are provided in the outcomes and results section of clinicaltrials.gov.

Table 3. Outcomes assessed for each hypothesis

Outcome type	Outcome Variable name		H2	НЗ	H4	Н5а	H5b	Н6а	H6b
Primary	Self-efficacy to Quit Smoking	Χ		Χ	Х			Χ	Х
Primary	Self-efficacy to Cut Down on Smoking	Χ		Χ	Χ			Χ	Χ
Primary	Worry About Harms from Smoking		Χ			Χ	Χ		
Primary	Strength of Feeling About Smoking		Χ			Χ	Χ		
Primary	Extent of Motivation to Quit	Χ	Χ	Χ	Χ	Χ	Χ	Χ	Χ
Primary	Talk About Smoking Cessation or Harms	Χ	Χ	Χ	Χ	Χ	Χ	Χ	Χ
Primary	Foregoing/stubbing out a Cigarette	Χ	Χ	Χ	Χ	Χ	Χ	Χ	Χ
Secondary	Strength of Hopefulness About Quitting	Χ		Χ	Χ			Χ	Χ
Secondary	Satisfaction From Smoking		Χ						
Secondary	Cognitive Elaboration of Smoking Benefits		Χ						
Secondary	Cognitive Elaboration of Smoking Harms		Χ			Χ	Χ		
Secondary	Cognitive Elaboration of Cessation Benefits	Χ		Χ	Χ			Χ	Χ
Secondary	Response Efficacy	Χ		Χ	Χ			Χ	Χ
Secondary	Perceived Susceptibility to Smoking Harms		Χ			Χ	Χ		
Secondary	Expressed Reactance Against Messages	Χ	Χ		Χ	Χ	Χ		
Secondary	Cigarettes Per Day (number of cig logs)	Χ	Χ	Χ	Χ	Χ	Χ	Χ	Х

X=included in the results data tables; results for outcomes that are not specific to hypotheses (i.e., no "X" in table above) are presented in data tables at the end of this document (see Appendix 1).

Assumptions for calculating power:

This section describes our assumptions regarding power before we collected our data. Throughout our discussion of power related to the statistical tests to evaluate our hypotheses of interest, we assume a moderate within-person autocorrelation of ρ = 0.40 for repeated measures. This estimate was lower than in the data we collected for this project (mean ICC=0.73) and in our re-assessment of preliminary data (mean ICC=0.72). Instead of running simulation programs to estimate power for mixed effects generalized linear models, we calculate the effective number of independent observations and use power for independence models.

Effective sample size: The effective number of independent observations $N_{\rm eff}$ is related to the number of correlated observations $N_{\rm eff}$ and the autocorrelation of correlated observations ρ as $N_{\rm eff} = N(1-\rho)/(1+\rho)$. Thus, our power calculations are derived using independence models with $N_{\rm eff} = 3N/7$ observations. Table 4 shows the effective sample for each hypothesis and data type, including adjustment for 10% and 20% missing data.

Table 4. Effective sample size for each hypothesis and data type, including missing data effects

				$N_{ m eff}$			
	Rep.			0% missing 10% missing 20% miss			
Data	Measures	Hypotheses	N	data	data	data	
Type 1	14	H1/H2	2,240=160*14	960	864	768	
	14	H3 ^{a-b} /H4 ^{a-b} /H5 ^{a-b} /H6 ^{a-b}	1,120=80*14	480	432	384	
Type 2	56	H1/H2	8,960=160*56	3,840	3,456	3,072	
	56	H3 ^{a-b} /H4 ^{a-b} /H5 ^{a-b} /H6 ^{a-b}	4,480=80*56	1,920	1,728	1,536	

We use the numbers in Table 4 as inputs for independent observations in deriving the detectable effect. In what follows, we report ranges of detectable effect sizes from 0% to 20% missing data in complete-case analyses. This presentation notwithstanding, our data analysis will employ multiple imputation methods to replace missing data, and we will investigate sensitivity models to determine whether missingness is related to any of the outcomes or covariates (See **Missing Data**, below).

Alpha: Modifications of the level of significance are considered using Bonferroni adjustment to maintain an overall 0.05 level of significance. As most of our hypotheses involve assessing 6 primary outcomes for each of the two data types, we use a Bonferroni-corrected $\alpha = 0.05/6 = 0.0083$.

Effects size referents: We follow Cohen's standardized effect sizes of small=0.20, medium=0.50, and large=0.80.¹ Standardized effect sizes are absolute differences divided by the standard deviation.

Power: Power was fixed to 80% in all analyses.

Analyses: Most detectable effect sizes were calculated using PASS 2012 software from NCSS (Kayesville, Utah). The only exception is for a hypothesis of mediation. In that case, we used the *powerMediation* package for *R* software. Specifically, we utilized the *minEffect.SLR* method to determine the minimum detectable slope (effect).

All detectable effect sizes were calculated for power=80% and stated level of significance. Furthermore, we assessed detectable effect sizes for the planned data collection design, up to 10% missing data, and up to 20% missing data (see Table 4).

Statistical design:

To test our study hypotheses (see Table 2, from Research Plan), we estimated a series of mixed effects generalized linear models, adjusting for repeated measures. The specific model we used depended on the type of dependent variable in the model. For each hypothesis, we estimated mixed effect generalized linear model of the outcome as a function of the inverse link: mixed-effects ordered logistic regression with inverse logit link for continuous/ordinal measures; mixed-effects regression with identity link for continuous/ordinal measures; negative binomial regression with log link for count measures; and mixed-effects logistic regression with inverse logit link for binary measures. Also, for outcomes with response options from 1 to 7, we estimated both mixed effects linear regression and ordered logistic regression models; however, we only report the results for the ordered logistic regression due to concerns about the distribution of responses and because the results are consistent across models. Note that the one count measure that we evaluate (i.e., cigarettes per day) is a single measure for each person and so there are no repeated measures. Evaluation of hypotheses will involve inference from Wald tests of associated regression parameters. We present power calculations for each hypothesis along with the model used to conduct the statistical tests. Subsequently, we discuss missing data and sensitivity analyses.

Throughout the following sections, we present models using the following indicator variables:

InsY _i	Person i has cigarette packages with inserts
$PicY_i$	Person i has cigarette packages with HWLs that include text and pictures
SeHi _i	Person i has a high baseline self-efficacy measure
EdHi _i	Person i has a high baseline education measure
$LtHi_i$	Person i has a high baseline literacy measure

Similarly, we also use the following indicator variables:

InsN _i	Person i has cigarette packages without inserts
$PicN_i$	Person i has cigarette packages with HWLs that include text only
$SeLo_i$	Person i has a low baseline self-efficacy measure
$EdLo_i$	Person i has a low baseline education measure
$LtLo_i$	Person i has a low baseline literacy measure

Model 1:

$$y_{ij} = g^{-1} \big[\beta_0 + (InsN_i \times PicN_i)\beta_1 + (InsN_i \times PicY_i)\beta_2 + (InsY_i \times PicN_i)\beta_3 + (InsY_i \times PicY_i)\beta_4 + Z_{ij}\tau + \gamma_i + \epsilon_{ij} \big]$$

where g^{-1} is the inverse link function (identity for continuous measures, log for count measures, and inverse logit for binary and ordinal measures), Z_{ij} is a possibly time-varying vector of covariates (e.g., sex, race, age, nicotine dependence, quit intentions), and y_{ij} is the outcome for the ith person at the jth repeated measure. This model will be used for evaluating Hypotheses 1 ($\mu_{InsN} = \mu_{InsY}$), 2 ($\mu_{PicN} = \mu_{PicY}$), 3a ($\mu_{PicN,InsY} = \mu_{PicY,InsY}$) & 4a ($\mu_{PicY,InsY} = \mu_{PicY,InsY}$) as shown in Table 5.

Table 5. Hypotheses evaluated using Model 1 and associated tests

Hypothesis	Test
Hypothesis 1	$H_0^1: \beta_1 + \beta_2 = \beta_3 + \beta_4$
Hypothesis 2	$H_0^2: \beta_1 + \beta_3 = \beta_2 + \beta_4$
Hypothesis 3a	$H_0^{3a}: \beta_3 = \beta_4$
Hypothesis 4a	$H_0^{4a}: \beta_4 = \beta_2$

Allowing up to 20% missing data, the range of effect sizes for which we will have 80% power to reject hypotheses are given by the values in Table 6 for the data type outcomes and specified level of significance.

Table 6. Level of significance and detectable effect sizes for all hypotheses

Hypotheses	Outcome	Level of significance	Range of effects*
H1 & H2	Type 1	$\alpha = 0.05/6 = 0.0083$	0.15 - 0.17
	Type 2	$\alpha = 0.05/6 = 0.0083$	0.07 - 0.08
H3a, H3b, H4a, H4b, H5a, H5b, H6a, H6b	Type 1	$\alpha = 0.05/6 = 0.0083$	0.22 - 0.24
	Type 2	$\alpha = 0.05/6 = 0.0083$	0.10 - 0.11

^{*}range of effects is for the different amounts of missing data (i.e., 0% - 20%)

Model 2a and Model 2b:

$$y_{ij} = g^{-1} \big[\beta_0 + InsN_i \beta_1 + \, InsY_i \beta_2 + Z_{ij} \tau + \, \gamma_i + \epsilon_{ij} \big]$$

Where g^{-1} is the inverse link function (identity for continuous measures, and inverse logit for binary and ordinal measures), Z_{ij} is a possibly time-varying vector of covariates (e.g., sex, race, age, nicotine dependence, quit intentions), and y_{ij} is the outcome for the ith person at the jth repeated measure. The 2a and 2b models are stratified over whether pictures were included (2a) or not (2b). This model will be used to assess Hypothesis

 $3b - H_0^{3b}$: $\mu_{InsN} = \mu_{InsY}$. Associated power is shown in Table 6. Note that the stratified analyses in Models 2a and 2b are investigated only if H_0^{3a} is rejected.

Note: H_0^{3a} was never rejected.

Model 3a and Model 3b:

$$y_{ij} = g^{-1} [\beta_0 + PicN_i\beta_1 + PicY_i\beta_2 + Z_{ij}\tau + \gamma_i + \epsilon_{ij}]$$

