Expressed Reactance Against Messages ⁵	1.21	0.78	0.35	4.25	0.76

^{*}All results from ordered logistic regression mixed effects models except for "Expressed reactance" which shows Odds Ratio for logistic regression mixed effects model.

^{1.} response options=1 Not at all – 7 Extremely; 2. response options=1 very BAD – 7 Very GOOD; 3. response options=1 Not at all – 7 All the time; 4. 1 No chance – 7 Certain to happen.

^{1.} response options=1 Not at all -7 Extremely; 2. response options= 1 Not at all -7 All the time; 3. 1 No chance -7 Certain to happen.

^{1.} response options=1 Not at all - 7 Extremely; 2. response options=1 very BAD - 7 Very GOOD; 3. response options=1 Not at all - 7 All the time; 4. 1 No chance - 7 Certain to happen. 5. Response options=yes, no

Table 4. Hypothesis 4. Results for outcomes not specific to hypothesized effects

Outcome Variable name	Coef*	SE	95% CI LB	95% CI UB	p-value
Worry About Harms from Smoking ¹	-0.12	0.84	-1.77	1.53	0.88
Strength of Feeling About Smoking ²	-0.08	0.68	-1.41	1.26	0.91
Satisfaction From Smoking ¹	-0.07	0.56	-1.17	1.03	0.90
Cognitive Elaboration of Smoking Benefits ³	0.23	0.49	-0.74	1.19	0.65
Cognitive Elaboration of Smoking Harms ³	0.18	0.49	-0.78	1.14	0.71
Perceived Susceptibility to Smoking Harms ⁴	-0.15	0.66	-1.45	1.15	0.82

^{*}All results from ordered logistic regression mixed effects models

Table 5a. Hypothesis 5a. Results for outcomes not specific to hypothesized effects

Outcome Variable name	Coef*	SE	95% CI LB	95% CI UB	p-value
Self-efficacy to Quit Smoking ¹	0.50	0.97	-1.41	2.41	0.61
Self-efficacy to Cut Down on Smoking ¹	0.35	0.95	-1.50	2.21	0.71
Strength of Hopefulness About Quitting ¹	1.18	1.25	-1.27	3.62	0.35
Satisfaction From Smoking ¹	-0.31	0.79	-1.85	1.24	0.70
Cognitive Elaboration of Smoking Benefits ²	0.54	0.60	-0.64	1.72	0.37
Cognitive Elaboration of Cessation Benefits ²	0.37	0.67	-0.94	1.69	0.58
Response Efficacy ³	-0.42	0.77	-1.92	1.09	0.59

^{*}All results from ordered logistic regression mixed effects models

Table 5b. Hypothesis 5b. Results for outcomes not specific to hypothesized effects

Outcome Variable name	Coef*	SE	95% CI LB	95% CI UB	p-value
Self-efficacy to Quit Smoking ¹	0.57	1.38	-2.15	3.28	0.68
Self-efficacy to Cut Down on Smoking ¹	0.08	1.35	-2.56	2.73	0.95
Strength of Hopefulness About Quitting ¹	-1.38	1.77	-4.84	2.09	0.44
Satisfaction From Smoking ¹	-0.05	1.12	-2.25	2.15	0.97
Cognitive Elaboration of Smoking Benefits ²	1.67	0.86	-0.01	3.35	0.05

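### H4's wording, its Table 3 outcomes and its Table 5 test do not agree: worry and feeling about smoking are left out, and no insert-by-picture interaction is tested on any outcome

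*SAP*

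**What the plan says.** The SAP (Study hypotheses and outcomes of interest) tests outcomes close to cessation behaviour under every hypothesis. For the remaining outcomes it gives a rule: "some outcomes were assessed only when they were relevant to the labeling effect (insert vs. pictorial HWL) evaluated in the hypothesis".

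Table 2 words three hypotheses as pictorial-warning effects:
- H2: "Exposure to packs with large pictorial HWLs will produce stronger negative affective responses toward smoking than text-only HWLs".
- H4: "Pictorial HWL effects (relative to text-only HWLs) on cessation-related outcomes (see H1) will be stronger when accompanied by inserts", with the reason "because inserts will promote efficacy beliefs and thereby reduce defensive responding".
- H5: "Pictorial HWL effects (relative to text-only HWLs) on key outcomes (see H1) will be moderated by baseline self-efficacy to quit".

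H3 is worded as an insert effect: "Insert effects on cessation-related outcomes (see H1) will be stronger when accompanied by pictorial HWLs than by text-only HWLs".

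In Table 3, "Worry About Harms from Smoking" and feeling about smoking (both primary) are marked under H2, H5a and H5b only. So are elaboration of smoking harms and perceived susceptibility (both secondary). Their results for H4 are in Appendix 1, under the title "Table 4. Hypothesis 4. Results for outcomes not specific to hypothesized effects".

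Table 5 gives the Model 1 tests: H3a is β3 = β4 and H4a is β4 = β2.

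**The concern.** If outcomes follow the labelling effect that a hypothesis evaluates, H4 should carry the pictorial-pathway outcomes, as H2 and H5 do. It carries the insert-pathway outcomes instead, and the SAP does not say why H4 and H5 differ.

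The protocol's conceptual model (section 2.2) makes synergy between inserts and pictorial warnings a central premise. Negative affect is the route by which pictures are said to work, and worry and feeling are two of the seven primary outcomes. As the plan stands, no main result shows whether inserts change the picture effect on either of them. No written test measures that change on any other outcome either.

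**Working it through.** **1. Table 3 columns side by side**

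| Outcome | H2 | H5a, H5b | H3 | H4 |
|---|---|---|---|---|
| Self-efficacy to quit; to cut down (primary) | – | – | X | X |
| Worry; feeling (primary) | X | X | – | – |
| Motivation; talk; foregoing/stubbing (primary) | X | X | X | X |
| Hope; elaboration of cessation benefits; response efficacy (secondary) | – | – | X | X |
| Elaboration of harms; perceived susceptibility (secondary) | X | X | – | – |
| Reactance (secondary) | X | X | – | X |

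H3 and H4 share the same five primaries. Over all outcomes they differ only by reactance (9 against 10). Against H5, H4 has the two self-efficacy outcomes in place of worry and feeling.

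**2. What Table 5 tests**

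Model 1 cells are β1 (no insert, text), β2 (no insert, picture), β3 (insert, text) and β4 (insert, picture).
- H3a, β4-β3, is the picture effect among packs with inserts.
- H4a, β4-β2, is the insert effect among packs with pictures.
- The change in one effect across levels of the other is β4-β3-β2+β1. This is not in Table 5. Models 2 and 3 are stratified and do not supply it, and H5b brings in baseline self-efficacy.

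By wording, H4 is the pictorial hypothesis; by written test, H3a is. On either reading one of the two evaluates a pictorial effect, and neither column contains worry or feeling.

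**3. What Appendix 1 implies**

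Assume that the H1 coefficient is the average insert effect, that H4a is the insert effect with pictures, and that both are signed insert minus no insert. Then the interaction is 2 × (H4a - H1). With equal, independent cell SEs of s, the SEs are s for H1, √2·s = 1.41s for a simple effect and 2s for the interaction. For the four outcomes below, SE(H4)/SE(H1) is 1.42 to 1.44, as expected of a simple effect set against an average.

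| Outcome | H1 (SE) | H4 | Interaction | SE ≈ 2 × SE(H1) | z |
|---|---|---|---|---|---|
| Worry | 0.77 (0.59) | -0.12 | 2(-0.12-0.77) = -1.78 | 1.18 | -1.51 |
| Feeling | -0.70 (0.48) | -0.08 | 2(-0.08+0.70) = +1.24 | 0.96 | 1.29 |
| Elaboration of harms | 0.59 (0.34) | 0.18 | 2(0.18-0.59) = -0.82 | 0.68 | -1.21 |
| Perceived susceptibility | 0.71 (0.46) | -0.15 | 2(-0.15-0.71) = -1.72 | 0.92 | -1.87 |

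No |z| exceeds 1.96; the largest corresponds to p of about 0.06. If the H4 coefficients alone are signed the other way, the interactions are worry 2(0.12-0.77) = -1.30, feeling 2(0.08+0.70) = +1.56, susceptibility 2(0.15-0.71) = -1.12 and harms 2(-0.18-0.59) = -1.54. Only the last, a secondary outcome, would then pass 1.96 (-1.54/0.68 = -2.26).

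**4. Alpha and precision**

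The SAP's 0.05/6 = 0.0083 reproduces, although every Table 3 column has five primaries. With worry and feeling added, H4 has seven: 0.05/7 = 0.0071.

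The detectable simple effect is √(2/n) × (z for two-sided α + z for 80% power), using the SAP's effective sizes for 0% to 20% missing data (n = 480 to 384 for Type 1, 1,920 to 1,536 for Type 2):
- At 0.0083: 0.225 to 0.251 (Type 1) and 0.112 to 0.126 (Type 2). Table 6 gives 0.22 to 0.24 and 0.10 to 0.11, without stating sidedness.
- At 0.0071: 0.228 to 0.255 and 0.114 to 0.127.

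An interaction needs √2 times as much: at 0.0071, about 0.32 to 0.36 (Type 1) and 0.16 to 0.18 (Type 2).

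**The case against.** The case for Table 3 as it stands has four parts.

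- **H4's named outcomes are covered.** H4 refers to the cessation-related outcomes of H1, which are discussion, foregoing, consumption and intention. Their Table 3 counterparts are all marked for H4. H5 speaks of key outcomes instead. This stands, and it defeats the inference that H4 rests on the wrong outcomes. It does not explain the swap, because self-efficacy is not among those four either, and H4 and H5 both refer back to H1.
- **H4's mechanism is efficacy.** The stated reason is efficacy beliefs and less defensive responding, and the SAP text groups H4 with H1 when it assigns reactance. This justifies keeping the efficacy outcomes and reactance. It does not by itself explain why H4 is treated differently from H5. The grouping is also a weak guide, since Table 3 marks reactance for H2 and H5 as well.
- **The written H4a test is an insert effect**, for which insert-pathway outcomes fit the rule. That is correct, but it moves the mismatch rather than removing it: the test then disagrees with H4's wording, and H3a becomes a picture effect without picture outcomes.
- **Nothing is hidden.** All four omitted outcomes are reported for H4 in Appendix 1, as the SAP announces.

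A reader might also infer that H4 merely duplicates H3. The documents do not support this. H3a and H4a are different simple effects with different results (worry -1.22 against -0.12), and H4 adds reactance. The two would coincide, on shared outcomes, only if both were tested as the interaction.

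**Conclusion.** The inconsistency is real but limited. H4's wording, its outcome list and its test point to different labelling effects. Two of seven primary outcomes and two secondary outcomes are left out of H4 without a stated reason for treating it differently from H5. Marking cells in Table 3 would not by itself create a test of synergy: that is missing because Table 5 contains no interaction contrast for any outcome.

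Under the sign convention assumed above, the four implied interactions point away from synergy. A reader might take this as evidence against H4, but the documents do not support that. None reaches p<0.05, the sign convention is not stated (reversing H1 and H4 together would flip every direction), and the SEs assume equal, independent cells. These figures show only that the answer is obtainable and currently absent from the main results.

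**What to change.** 1. State which labelling effect H4 evaluates, and bring its Table 2 wording, Table 3 column and Table 5 test into line.
2. Keep H4's efficacy outcomes and reactance. Add worry and feeling as primaries, and elaboration of harms and perceived susceptibility as secondaries.
3. Test H4 on all its outcomes, not only the added ones, with β4-β3-β2+β1 from Model 1, so that the family has one estimand. Give the sign convention. Keep the H4a results as the test written in this version.
4. Use 0.05/7 = 0.0071 for the seven H4 primaries.
5. Label the change post hoc. This version, dated December 13, 2022, both clarifies Table 3 and reports results.

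The work is a table edit and one contrast per outcome from a model already in the plan. The stricter alpha costs little (Type 1 detectable simple effect 0.225–0.251 becomes 0.228–0.255). The larger cost is precision: the interaction's SE is √2 times that of the simple effect it replaces, so a null result would be weak evidence against synergy.

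### Holm's step-down procedure would hold the SAP's 0.05 within each hypothesis, never reject less than its fixed Bonferroni 0.0083, and gain power when several effects are real

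*SAP*

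**What the plan says.** The multiplicity statement is in the SAP under Assumptions for calculating power, Alpha: "Modifications of the level of significance are considered using Bonferroni adjustment to maintain an overall 0.05 level of significance". The divisor is explained next: "As most of our hypotheses involve assessing 6 primary outcomes for each of the two data types, we use a Bonferroni-corrected" level of 0.05/6 = 0.0083. Table 6 ("Level of significance and detectable effect sizes for all hypotheses") repeats 0.0083 for every hypothesis and both data types.

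The Statistical design section names the test but no threshold: "Evaluation of hypotheses will involve inference from Wald tests of associated regression parameters". No step-down or other sequential rule appears.

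On the number of outcomes, the SAP says "Table 3 lists all primary and secondary outcomes, showing which were assessed for each hypothesis". Every column of that table, H1 to H6b, marks five primary outcomes. Two are daily (talk, foregoing/stubbing). Three are event-based: the two self-efficacy items and motivation for insert hypotheses, or worry, feeling and motivation for pictorial-warning hypotheses.

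**The concern.** Single-step Bonferroni holds each outcome to 0.0083 whatever the other outcomes show. Holm uses the same p-values, also needs no correlation assumption, and relaxes the level after each rejection. At equal error control it can only reject the same outcomes or more.

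This matters here because H1 and H2 each predict a pattern: efficacy beliefs or negative affect shift, and cessation-related outcomes follow. If such a pattern is real, several outcomes in one hypothesis should move together, which is where Holm gains most. A secondary outcome of that pattern with, say, p = 0.012 fails at 0.0083. Under Holm it could be claimed within the same 0.05 once stronger outcomes had passed.

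**Working it through.** **Inputs.** Overall level 0.05, divisor 6 and level 0.0083 (SAP, Alpha); five primary outcomes per hypothesis (SAP, Table 3); "Power was fixed to 80% in all analyses" (SAP, Power). Assumed: two-sided Wald tests, since sidedness is not stated, and a common correlation between the five test statistics of 0, 0.3, 0.5 or 0.7, since none is given.

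**The plan's figure.** 0.05/6 = 0.00833, as stated. Five tests at that level spend at most 5 × 0.00833 = 0.0417 per hypothesis.

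**Holm levels.** The k-th smallest p-value is compared with 0.05/(D − k + 1), stopping at the first failure.

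- D = 6 with five tests: 0.0083, 0.0100, 0.0125, 0.0167, 0.0250.
- D = m = 5: 0.0100, 0.0125, 0.0167, 0.0250, 0.0500.

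**Why Holm cannot reject less.** If a p-value is at or below 0.05/D, so is every smaller one. All Holm levels are at least 0.05/D, so each is passed and the outcome is rejected.

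**Why the error holds.** With m0 true nulls, the first null reached in the ordering faces a level of at most 0.05/m0. The chance that any of the m0 nulls falls below that is at most 0.05, whatever the correlation.

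**Power.** A real effect with 80% power at 0.0083 has non-centrality z(1 − 0.00833/2) + z(0.80) = 2.638 + 0.842 = 3.480. At a fixed 0.01 its power is Φ(3.480 − 2.576) = Φ(0.904) = 0.817. The Holm columns come from simulation (400,000 replicates per setting); ranges run over the four correlations.

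| Real effects of five | Bonferroni 0.0083 | Holm, D = 6 | Bonferroni 0.01 | Holm, m = 5 |
|---|---|---|---|---|
| 5 | 80% | 85-88% | 82% | 88-92% |
| 3 | 80% | 82-83% | 82% | 84-85% |
| 2 | 80% | 81% | 82% | 83% |
| 1 | 80% | 80% | 82% | 82% |

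Entries are average power per real effect. No replicate contained a Bonferroni rejection that Holm missed at the same divisor. With no real effects, the chance of any false claim is identical for the two methods at the same divisor: 0.030-0.041 (D = 6) and at most 0.049 (m = 5). With three real effects, Holm's chance of a false claim is at most 0.03 (D = 6) and 0.044 (m = 5).

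**How secure is the 80% baseline?** It is the SAP's premise, and it looks optimistic in two respects.

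- For H1/H2 daily data with no missing data, the two-sided detectable effect is 3.480 × √(2/960) = 0.159, against 0.15 in Table 6. Over all rows of Table 6, power at the stated effects comes out at 66-78%.
- The SAP assumed a within-person correlation of 0.40 and reports an observed mean ICC of 0.73. With an exchangeable design effect, N_eff per group is 2,240/(1 + 13 × 0.73) = 213.5. At d = 0.20, power at 0.0083 is Φ(0.20 × √(213.5/2) − 2.638) = Φ(−0.572) = 28%. With five real effects and correlation 0.5 between tests, Holm gives 33% (D = 6) or 37% (m = 5). At 0.0083 nothing is rejected 39% of the time, and Holm with D = 6 then gains nothing.

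**The case against.** **Bonferroni is valid, so this is a preference.** The first half stands: no error-rate failure or bias is shown. But Holm needs no extra assumption and costs nothing in error, so it is a concrete improvement rather than a matter of taste.

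**0.0083 is a planning input, not a decision rule.** The section introduces itself with "This section describes our assumptions regarding power before we collected our data", and the analysis section gives no threshold. Reading 0.0083 as the rule is therefore an inference. It is nonetheless the only level stated, and its declared purpose is to hold an overall 0.05. If it is not the rule, the SAP has none, and the proposed sentence fills that gap.

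**The change comes after the results.** This stands and limits the remedy. The SAP is dated 13 December 2022, data collection ended in June 2021, and the document reports results, including that the H3a and H4a nulls were never rejected. If those were judged at 0.0083 or anything looser, Holm with divisor 6 adds nothing there.

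**Bonferroni has simple simultaneous confidence intervals and Holm does not.** This also stands. Appendix 1 prints unadjusted 95% intervals, but it covers only outcomes outside each hypothesis. The hypothesised results are tabulated elsewhere, so whether adjusted intervals were used there cannot be checked.

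**The family is debatable.** The SAP counts outcomes by data type, whereas pooling daily and event-based outcomes gives five. Six matches neither count in Table 3. Correcting the divisor to 5 alone brings power to about 82% without Holm.

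**Conclusion.** The point holds as a modest improvement to a valid plan. Within one hypothesis, Holm keeps the 0.05 and never rejects less at the same divisor. If every effect is real, average power rises by about 5-8 points with divisor 6 or 8-12 points with m = 5. With three real effects the rise is 2-3 or 4-5 points. With one it is zero or about 2 points. These sizes rest on the SAP's 80% at 0.0083, two-sided tests and assumed correlations of 0 to 0.7.

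Three stronger readings are tempting but not supported:

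- That power on four of the five outcomes is thrown away. No fixed set of outcomes loses power; Holm relaxes only after a rejection.
- That the trial needs all five outcomes to reject, so the gain in detecting all five together is the relevant figure. The SAP states no such rule.
- That Holm would secure 0.05 for the whole trial. H1, H2, H3a, H4a, H5a and H5b, plus H6a and H6b with three moderators each, make 12 families of five, or 60 tests. Their 0.0083 levels sum to 0.50. Applied per hypothesis, neither method controls error across H1-H6.

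**What to change.** In the Alpha paragraph, define the family as the primary outcomes marked in Table 3 for each hypothesis (m = 5), and say whether each H6 moderator is its own family. Then apply Holm to the Wald p-values: smallest against 0.05/5, next against 0.05/4, and so on, stopping at the first failure. Table 6 should keep a single first-step level as the worst case. That is 0.01 for m = 5; the printed 0.0083 is slightly stricter and can stand as the pre-data record.

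Date the change and label it post hoc. Report Holm-adjusted p-values, to at least three decimals, beside the Bonferroni 0.0083 decisions, so a reader can see any outcome whose status differs and that the difference arose from a rule chosen after results were known. State that control is within each hypothesis only.

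The work is a short addition to the text and a re-reading of existing p-values, with no new data and no refitting. The costs are the post hoc status and the lack of simple simultaneous intervals to match Holm's decisions.
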